Studies on prevention of recurrent infections have been disappointing. Most SSTI prevention efforts have focused on body decolonization of *S. aureus*. Typical decolonization regimens have involved combined nasal and skin decontamination. For example, Fritz et al. randomized children with SSTIs to either skin decolonization with chlorhexidine (CHG) and nasal decolonization with mupirocin of the affected child or CHG skin decolonization + mupirocin given to the whole household.⁸ While decolonization of the whole household was superior (54% SSTI recurrence rate vs. 72% during the 12 month follow up period), the trial had disappointing results in that even in the more aggressively treated group, recurrence rates of SSTIs in the affected children exceeded 52%. The results suggest that even skin and nasal decolonization is insufficient to prevent recurrent SSTIs in children. Another recent study by Kaplan et al. randomized children with SSTIs, most caused by CA-*S. aureus* infections to bleach baths versus routine daily hygienic measures.¹⁶ Unfortunately, the skin decolonization afforded by bleach baths did not result in a decrease rate of recurrent SSTIs compared with routine daily hygienic measures (17% vs. 21%, $P=0.15$).¹⁶ These findings suggest that skin decolonization is ineffective at prevention of recurrent *S. aureus*-associated SSTIs. Clearly, more effective means of decolonization are needed to further decrease rates of recurrent infections.

Data from our group and others have demonstrated that extra-nasal *S. aureus* colonization is much more common than previously believed.^{17,18} We found that among household contacts of children and adults with *S. aureus* SSTIs, the most common body site of *S. aureus* colonization on the human body is not the anterior nares (nose) but the oropharynx.¹⁸ In this study, conducted in Los Angeles and Chicago, 30% of household contacts were colonized with *S. aureus* in the oropharynx, but only 25% in the nares.

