The body site of greatest *S. aureus* colonization has traditionally been believed to be the anterior nares.^{40,41} *S. aureus* has been known to colonize the axilla, perineum, rectum, vagina, and the throat (oropharynx).⁴²⁻⁴⁵ However, only recently have data regarding the importance and scale of non-nasal colonization been appreciated.⁴²⁻⁴⁵ An investigation conducted by our group in an area of high MRSA endemicity found that among persons with *S. aureus* SSTIs cultured at the anterior nares, oropharynx, and inguinal region, *S. aureus* colonized 40% (137/350) and 50% (405/812) of their household contacts.¹⁸ A nares-only survey would have missed 48% of *S. aureus* and 51% of MRSA colonized persons.¹⁸ Among the subset of patients with CA-MRSA infection, the proportion of oropharyngeal-only colonization was 12%, suggesting nasal-only screening for *S. aureus* colonization misses a sizable proportion of colonized patients with community onset SSTI. In fact oropharyngeal colonization was more prevalent than nasal colonization (26.0% vs. 24.0%) in our cohort of >1000 persons.¹⁸ Investigations of patients with acute skin infections and other populations at high risk for *S. aureus* infection by our group and others have demonstrated the prevalence of *S. aureus* oropharyngeal colonization are similar or exceed that of nasal colonization.^{17,43,44,46-49}

The failure of nares plus body decolonization at decolonizing patients and preventing recurrent *S. aureus* infections is disappointing. However, as outlined above, major efforts to prevent infection have employed mupirocin plus CHG (or bleach).^{8,16} Both nasal and body decolonization are well-established methods to decrease *S. aureus* in hospitalized patients.⁵⁰⁻⁵³ However, data on the efficacy of oral CHG rinses to eliminate oropharyngeal *S. aureus* colonization are extremely limited. Those few data that exist are from adults, largely elderly adults;¹⁹ thus the applicability of these limited data to children is unclear. **To truly perform studies of comprehensive *S. aureus* decolonization, oropharyngeal *S. aureus* colonization must be addressed therapeutically. However, there are few data on the efficacy of CHG at oropharyngeal *S. aureus* eradication and none in children.** If CHG is found to be effective in children, strategies that incorporate oropharyngeal decolonization as part of a more global eradication strategy may be critical for *S. aureus* SSTI prevention.

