Figure 2. Timeline of Study Activities

[figure not shown]
Activities	Year 1	Year 2
Ramp-up of investigation, IRB submission, development of study protocol, analysis plan, and databases		
Recruitment/Enrollment of Subjects		
Follow-up of Subjects		
Whole Genome Sequencing of S. aureus and MRSA Isolates		
Data analysis and interpretation, manuscript preparation and submission, study close-out		

Enrollment of a cohort of pediatric patients with *S. aureus* skin and soft tissue infection

Enrollment

We will enroll 240 subjects with a history of SSTI in the Pediatric Emergency Department (PED) at Harbor-UCLA Medical Center. Subjects who meet the inclusion and exclusion criteria outlined below will undergo rapid screening for oropharyngeal *S. aureus* colonization. Assuming a 25% oropharyngeal colonization prevalence,¹⁸ 60 subjects will have oropharyngeal colonization with a *S. aureus* and be eligible for the trial's decolonization regimen (Figure 3).

Figure 3. Screening of Subjects for Enrollment

query PED physicians, and nursing staff about potentially interested patients (e.g., those with a history of SSTIs) whose parents/guardians are willing to discuss possible participation in a study. PED staff will also be in-serviced about the study and encouraged by our PED physician Co-Investigator to call study coordinators as needed. To complement these efforts, flyers will be placed in the PED advertising to medical staff to call or page study coordinators about potentially eligible patients. These strategies have been highly successfully at each of the sites for enrolling subjects with SSTIs in the PED for our previous investigations. Once an interested patient is identified, the study coordinator will complete the informed consent process in a private setting in the patient's parent/guardian preferred language (English or Spanish).

Inclusion and Exclusion criteria

For this investigation, we will use strict inclusion and exclusion criteria. Inclusion criteria will include:

- History of skin or soft tissue infection, as per patient report
- Age \geq 5 years and $<$ 18 years.
- Able to gargle (if needed, ability to gargle can be assessed at screening using water).
- Willing and able to undergo nares and oropharyngeal swabbing.
- Able to come to the research clinic for study follow-up visits for the study period.

Exclusion criteria for subjects will include:

- Suspected or confirmed infection requiring systemic antibiotics.

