Once a patient consents to study participation, study coordinators will obtain a specimen from the subject's nares, and oropharynx for both rapid testing and standard culture based testing. A research assistant will then process the swab for rapid molecular testing (GeneXpert MRSA/SA platform) to determine if the purulent fluid has MRSA, MSSA, or neither. The sensitivity and specificity of this FDA approved assay in the nares are 97 and 96%, respectively,⁶⁵ sensitivity for throat specimens is 75%-81% with a very high sensitivity of 98%.^{87,88} The specimen will be processed in the [name] Laboratory on the Harbor-UCLA Medical Center campus, which is a <5 minute walk from the PED. Rapid molecular testing results will be available within one hour and conveyed to the subject. Participants who are negative for *S. aureus* oropharyngeal colonization will be told they are not eligible for the intervention and discontinued from the study.

Participants who are positive for *S. aureus* oropharyngeal colonization will be allowed to participate in the trial and data collection will commence. Of note, participants who are rapid test positive for *S. aureus* and later using clinical microbiology lab testing with culture-based methods are found to be negative for *S. aureus* will not be included in the analysis, although given the very high sensitivity of the GeneXpert assay in throat specimens (98%), we think this is an unlikely event⁸⁷ and these events are built into our expected attrition rate (see below). For ethical purposes, all subjects, regardless of rapid testing results, will receive educational materials regarding optimal hygienic practices to reduce risk of transmission, basic education about *S. aureus*, SSTI, and recognition of warning signs of serious skin infections. These materials were developed for previous investigations and available in English and Spanish.

Based on previous investigations of patients with a history of skin infection from our group,¹⁸ we estimate 33% of children with a history of SSTIs will be positive for *S. aureus* (n=80, Figure 2). Assuming a 75% sensitivity of the GeneXpert assay, and 75% of those participants (n=60) will be positive at the oropharynx (see section on Power and Sample size, below). Study coordinators will complete the baseline visit for participants who are *S. aureus* positive on rapid molecular testing.

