Using an alpha of 0.05 and expected cure rates of 50% and 10% in the CHG and placebo arms respectively, 54 subjects (27 per group) would be needed for 85% power to detect a 40% absolute difference in cure ($p<0.05$) between groups. Correcting for a 10% attrition rate, 60 enrolled subjects would be needed. To identify 60 subjects with oropharyngeal colonization, and assuming 33% of patients who are high risk for *S. aureus* colonization will have oropharyngeal colonization, 240 subjects will need to be screened to obtain 80 patients that are oropharyngeally colonized with *S. aureus*. Of these, 75% (n=60) will have *S. aureus* detected by the GeneXpert rapid test and will undergo randomization.

Data Analyses and Data and Safety Monitoring

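### The 33% throat-carriage rate that turns 240 screened into 60 randomized is reported for no group in the documents; the rates they report or imply for 17% to 30% carriage give about 30 to 54

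*Combined protocol and SAP*

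**What the plan says.** Three sections set out how many children must be screened.

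- **Enrollment** (Experimental Design and Methodology): "Assuming a 25% oropharyngeal colonization prevalence", citing reference 18, 240 children give 60 eligible. No test-detection step is applied.
- **Baseline visit**: a 33% *S. aureus* rate (n=80) is introduced with "Based on previous investigations of patients with a history of skin infection from our group", again citing reference 18. A 75% rapid-test sensitivity then brings the 80 down to 60.
- **Power and Sample Size** (Aim 1): "assuming 33% of patients who are high risk for *S. aureus* colonization will have oropharyngeal colonization", so that "240 subjects will need to be screened to obtain 80 patients that are oropharyngeally colonized". The rapid test detects 75% of these, 60 are randomized, and 10% attrition leaves 54 (27 per arm, 85% power at 50% versus 10%).

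On the cited cohort, Supportive Preliminary Data gives carriage at any of three sites: *S. aureus* "colonized 40% (137/350) and 50% (405/812) of their household contacts", the first figure being for the infected patients. It also states: "In fact oropharyngeal colonization was more prevalent than nasal colonization (26.0% vs. 24.0%) in our cohort of >1000 persons". The Scientific Abstract describes the same 26% versus 24% as covering infected persons together with their household members. Background and Significance says "30% of household contacts were colonized with" *S. aureus* in the throat, and gives 31% for a subset of 268 contacts. In the reference list, the title of reference 18 concerns household contacts of patients with skin infections.

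**The concern.** The trial screens children who have themselves had a skin infection. The throat rates reported from the cited cohort describe other people: household contacts alone, or a pool in which contacts are 812 of 1,162 (70%). No throat rate is given for the 350 patients, and no throat rate of 33% is given for anyone.

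The direction of the error matters. If contacts carry at 30% and the pool at 26.0%, the patients must lie below 26%. The whole chain from 240 to 60 to 54 depends on this rate. If it is too high, 240 screened will not supply the sample on which the 85% power was calculated.

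This is separate from the disagreement between 25% and 33%. Settling on either number would still leave open whether it describes the children being screened.

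**Working it through.** **1. The plan's own chain.** 240 × 1/3 = 80; 80 × 0.75 = 60; 60 × 0.90 = 54. The Enrollment route, 240 × 0.25, also gives 60. A continuity-corrected two-proportion formula at 50% versus 10%, two-sided 0.05 and 85% power gives 27 per arm, as stated. Exact two-sided Fisher power at 27 per arm is 87.2%. (The plan names Fisher's test but not its sidedness; two-sided is assumed throughout.) The plan's arithmetic is sound, so the question is the input rate.

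**2. Does 33% fit the cohort?** With contacts at 30%, a patient rate of 33% would make the pooled rate (0.33 × 350 + 0.30 × 812) / 1,162 = 30.9%. A patient rate of 25% would make it 28.5%. The reported pooled rate is 26.0%.

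**3. Patient rate by subtraction.** Inputs: 26.0% pooled, 30% in contacts, 350 patients, 812 contacts.

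(0.260 × 1,162 − 0.30 × 812) / 350 = (302.1 − 243.6) / 350 = 58.5 / 350 = 16.7%.

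Rounding of the two percentages (25.95–26.05% and 29.5–30.5%) allows 15.4% to 18.0%. Sampling error on about 58/350 is wider, roughly 13% to 21%. One percentage point in the contacts' rate moves the result by 812/350 = 2.3 points; one point in the pooled rate moves it by 1,162/350 = 3.3 points.

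**4. Cross-checks that do not use the pooled 26.0%.**

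- Adult decolonization trial (Project CLEAR), baseline throat carriage: 21% and 22%.
- Throat-only carriage of 12% in the CA-MRSA patient subset, with half of throat carriers not nasally colonized: 0.12 / 0.50 = 24%. The denominator of the 12% is unclear, and groin carriage is ignored.
- Any-site carriage is 137/350 = 39% in patients and 405/812 = 50% in contacts. About 243.6/405 = 60% of colonized contacts carry in the throat. The same share in patients gives 0.391 × 0.601 = 23.5%. A 33% throat rate would require 115.5/137 = 84%.

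**5. Yield of 240 screened and resulting power.** Randomized = 240 × rate × 0.75; completing = randomized × 0.90. Power is by full enumeration of the Fisher test at 50% versus 10%.

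| Throat rate | Basis | Randomized | Completing | Per arm | Fisher power |
|---|---|---|---|---|---|
| 16.7% | subtraction | 30 | 27 | 13–14 | 49–54% |
| 21% | adult trial, lower baseline | 38 | 34 | 17 | 63% |
| 24% | throat-only figure | 43 | 39 | 19 | 71% |
| 26% | pooled cohort | 47 | 42 | 21 | 76% |
| 30% | household contacts | 54 | 49 | 24 | 83% |
| 31% | contact subset | 56 | 50 | 25 | 83% |
| one third | plan | 60 | 54 | 27 | 87% |

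With the upper throat sensitivity given in the Baseline visit section (81%), 30% carriage gives 58 and 31% gives 60. At 75% detection, reaching 60 would take about 478 screened at 16.7%, 333 at 24% and 267 at 30%.

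**The case against.** **The 17% is not a measurement.** It is a difference between two rounded percentages and assumes that the 26.0% covers all 1,162 people; the text says only that the cohort exceeded 1,000. The cohort included adults, and its antibiotic status at swabbing is not given. Trial children must have had no systemic antibiotics for 28 days, and the Background says colonization persists in only about half of patients after systemic treatment. Recently treated patients could therefore understate carriage in trial children. All of this stands, so 17% is the low end of a range and not a replacement value.

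**The attribution to patients is not plainly false.** The cited cohort does contain 350 skin-infection patients, with 39% any-site carriage, and the Baseline visit sentence names no body site for its 33%. That is fair, and the origin of the 33% cannot be settled from the documents. But Power and Sample Size explicitly uses it as throat carriage. If it were an any-site rate, the throat rate would be lower still, which does not rescue the 60.

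**The shortfall depends on the detection step.** Without the 75% factor, as in Enrollment, the pooled 26% gives 240 × 0.26 = 62. But the plan applies that step in its sample-size calculation. Even without it, 16.7% gives about 40.

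**Power depends on completers, not on 240.** This also stands. Power and Sample Size states a need for 60, and the Human Subjects section only anticipates 240 over 18 months. Nothing says recruitment stops at 240, so a low yield is first a feasibility problem. Equally, nothing says recruitment continues beyond 240 or who would notice a low yield.

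**Conclusion.** The concern holds as a point about an unsupported input. The 33% is not reported as a throat rate for any group, and the cohort cited for it implies a rate below 26% in the patients themselves. At the plan's 75% detection, 17% to 30% carriage gives about 30 to 54 randomized. The 31% contact subset gives 56. With the detection step kept, 60 is reached only by combining that 31% with 81% sensitivity, the top of both ranges.

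A reader might infer that 240 screened will yield 30 and not 60, or that the trial will probably miss a true effect. The documents do not support either. Thirty is the low end and rests on the subtraction; the cross-checks suggest 38 to 43. Even at the low end, power of 49–54% is about even odds, and at contact-like rates power is 83%, close to the planned level. Every power figure below 87% also assumes that recruitment stops at 240.

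The conclusion rests on the pooled and contact rates coming from the same cohort, on 75% detection and 10% attrition as planned, and on a two-sided Fisher test.

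**What to change.** 1. In Enrollment, Baseline visit, and Power and Sample Size, state which population and body site each carriage rate describes.
2. Replace the 33% and the 25% with the throat rate of the 350 skin-infection patients, tabulated from the group's own data. Until that is available, give a range.
3. Restate the expected yield of 240 screened as about 30 to 54 randomized over 17% to 30% carriage, with the matching power.
4. State that recruitment is governed by the number randomized, and schedule an early check of observed yield (for example after the first 60 screened), in place of presenting 240 as sufficient for 60.

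The cost is protocol wording and one tabulation of data already held. The downside is that the stated yield and power become less favourable. If the early check shows a low yield, more screening or a longer enrollment period may be needed, and the plan should say so in advance.
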